## 5.6 Screen Failures

Screen failures are defined as subjects who consent to participate in the clinical study but are not subsequently randomised. To ensure transparent reporting of screen failure subjects, a minimal set of screen failure information will include demography, screen failure details (e.g. withdrawal of consent), eligibility criteria, and any adverse events as applicable.

Individuals who do not meet the criteria for participation in this study (screen failure) may not be re-screened.

## 5.7 Sponsor's Qualified Medical Personnel

Contact information for the sponsor's appropriately qualified medical/dental personnel or clinical research scientist for the study is documented in the Study Contact List located in the investigator study master file held at the study site.

The contact number is only to be used by study staff seeking advice on medical/dental questions or problems in the event that the established communication pathways between the study site and the study team are not available.

Property of GSK Consumer Healthcare - Confidential

May not be used, divulged, published or otherwise disclosed without the consent of  
 GSKCH

CCI ██████████ Clinical Protocol Template v7.0

Page 35 of 100

The contact number is not intended for direct use by study subjects. To facilitate access to appropriately experienced GSK CH personnel on study-related medical/dental questions or problems, subjects will be provided with a contact card. The contact card will provide, as a minimum, protocol identifiers, the subject's study identification number, contact information for the study site, and contact details in the event that the study site cannot be reached to provide advice on a medical question or problem identified by a healthcare professional other than the investigator.

### **5.8 Clinical Assessor Qualifications**

Examiners involved in screening and clinical assessment procedures will be qualified dentists, registered to practice in the UK. Oral examinations to determine subject eligibility and all safety/product performance (tactile threshold/ Schiff sensitivity scale) assessments will be performed by appropriately trained clinical examiners. No additional qualifications are required for the clinical examiners involved in this study.

## **6 STUDY PRODUCTS**

For the purposes of this study, per International Conference on Harmonisation (ICH) guidelines, and GSK policy, study intervention is defined as any investigational intervention(s), marketed product(s), placebo, or medical device(s) intended to be administered to a study participant according to the study protocol.

This includes a product with a marketing authorisation when used or assembled (formulated or packaged) in a way different from the approved form, or when used for an unapproved indication, or when used to gain further information about an approved use.

Property of GSK Consumer Healthcare - Confidential

May not be used, divulged, published or otherwise disclosed without the consent of  
GSKCH

CCI ██████████ Clinical Protocol Template v7.0  
Page 36 of 100

## 6.1 Study Product Supplies

The following study products will be supplied by Clinical Supplies Department, GSK CH.

**Table 6-1** **Investigational/Study Product Supplies**

Product Description	Acclimatisation Product	Test Product	Comparator 1	Comparator 2	Negative control
	Regular fluoride toothpaste	3% PVM/MA + 5% KNO 3 combination toothpaste	3% PVM/MA only toothpaste	5% KNO 3 only toothpaste	Regular fluoride toothpaste
Fluoride content	1450ppm fluoride as NaF	1450ppm fluoride as NaF	1450ppm fluoride as NaF	1450ppm fluoride as NaF	1450ppm fluoride as NaF
Product Name	Colgate Cavity Protection	N/A	N/A	N/A	Colgate Cavity Protection
Pack Design	One carton containing 2 overwrapped tubes of toothpaste				
Dispensing Details	Visit 1 (Screening): 1 carton	Visit 2 (Baseline): 2 cartons			
Product Master Formulation Code (MFC)	Commercial Product	CCI [REDACTED]	CCI [REDACTED]	CCI [REDACTED]	Commercial Product
Product Application	Subjects will dose the toothbrush provided with a strip of dentifrice (a full brush head) on each brushing occasion				
Route of Administration	Topical Oral Use				
Usage Instructions	Subjects will brush for one timed minute, twice daily (morning and evening); subjects will be permitted to rinse with water post-brushing.	Subjects will brush their two selected 'test teeth' first, followed by the whole mouth for one timed minute, twice daily (morning and evening); subjects will be permitted to rinse with water post-brushing.			
Return Requirements	All used/unused product to be returned to GSK				

Property of GSK Consumer Healthcare - Confidential

May not be used, divulged, published or otherwise disclosed without the consent of  
 GSKCH

CCI [REDACTED] Clinical Protocol Template v7.0

Page 37 of 100

**Table 6-2 Sundry Items**

Item	Supplied By	Pack Design	Dispensing Details	Return/Disposal Details	
				Used Samples	Unused Samples
Aquafresh, flat trim, medium toothbrush (Germany)	GSK CH	Individual toothbrush in commercial pack	One toothbrush at Screening for use with acclimatisation toothpaste  One toothbrush at Baseline for use with assigned study toothpaste	Destroy at site using site disposal procedures	Return to GSK
Countdown Timer	GSK CH	Individual timer in commercial pack	One timer at Screening visit	Subject to keep or destroy at site using site disposal procedures	Return to GSK
Pregnancy Tests (UK Market)	GSK CH	Commercial pack	Use as per study schedule	Destroy at site using site disposal procedures	Return to GSK

For further information, please refer to the Global Clinical Supplies (GCS) Packaging and Labelling Proposal. GSK CH will ensure copies of the diary (which will also include toothpaste usage instructions), the clinical assessment score sheets, the DHEQ-15, the NRS question and the Subject Contact Cards are provided to the study site.

Detailed instructions for the return of study product/study supplies for the accountability checks and subsequent destruction will be provided by GSK CH prior to the study close out visit.

### 6.1.1 Product Form and Packaging

All study products are toothpastes, intended for topical oral use, and will be applied by toothbrushing using a manual toothbrush.

The test product and comparator toothpastes will be manufactured and filled into plain white tubes by GSK CH with a study label affixed; the acclimatisation and control toothpastes will be supplied in their commercial packs. All study toothpastes (including

Property of GSK Consumer Healthcare - Confidential

May not be used, divulged, published or otherwise disclosed without the consent of  
 GSKCH

CCI

Clinical Protocol Template v7.0

Page 38 of 100

the acclimatisation product) will be overwrapped in white vinyl (to mask their identity and obscure any branding) with a study label affixed. The content of the product labels will be in accordance with all applicable regulatory requirements and will be the responsibility of the GSK CH GCS group. Each study label will contain, but not be limited to, protocol number, directions for use and storage requirements.

Each subject will receive sufficient tubes of the acclimatisation toothpaste and their assigned study toothpaste to cover usage during the acclimatisation and treatment periods, respectively. Acclimatisation toothpaste will be dispensed at Screening (Visit 1); study toothpaste will be dispensed at Baseline (Visit 2). Sundry items will be supplied in their commercial packaging for dispensing by study staff as required.

Care should be taken with the supplied products and their labels to ensure they are maintained in good condition; it is important that all labels remain intact and legible for the duration of the study. Subjects will be instructed to not remove or deface any part of a product label.

All products supplied are for use only in this clinical study and should not be used for any other purpose.

#### **6.1.2 Product Dispensing**

Subjects will be assigned to study product in accordance with the randomisation schedule generated by an approved GSK CH vendor, prior to the start of the study, using validated software.

The product dispensing area will be separate from the clinical examination area. Study toothpastes will be dispensed in blinded fashion to the subject, by trained site personnel. These staff members will not be involved in any safety/product performance assessments or other aspects of the study that could be influenced by the knowledge of product a subject has been assigned to. An additional member of the site staff will verify the dispensing procedure has been completed accurately for each subject.

A record of product dispensing to each subject will be maintained in the dispensing log; completion of the dispensing procedure will be recorded in the case report form (eCRF).

Property of GSK Consumer Healthcare - Confidential

May not be used, divulged, published or otherwise disclosed without the consent of  
GSKCH

CCI

Clinical Protocol Template v7.0

Page 39 of 100

## 6.2 Administration

Subjects will be instructed to self-administer the acclimatisation toothpaste and their assigned study toothpaste according to the usage instructions provided at the study site and detailed in the diary. To help ensure subjects fully understand the amount of toothpaste to be used each time they brush and the usage instructions:

- staff will demonstrate dispensing a full ribbon of toothpaste along the length of the toothbrush head to each eligible subject and supervise their first brushing with the acclimatisation toothpaste/diary completion at the end of the Screening visit (Visit 1), after all clinical assessments have been completed;
- staff will supervise the first brushing with study toothpaste/diary completion at the end of the Baseline visit (Visit 2), after all clinical assessments have been completed;
- staff will supervise a brushing with study toothpaste/diary completion at the end of the Day 3, Week 2, 4 and 8 visits (Visits 3-6), after all clinical assessments have been completed.

On-site administration of study products will be recorded in the dispensing log and the eCRF.

### 6.2.1 Product Usage Errors

Study product usage errors may result, in this study, from the administration or consumption of the wrong product, by the wrong subject, at the wrong time, in the wrong way.

Such study product usage errors occurring to a study subject are to be captured in the eCRF. In the event of study product usage error, the sponsor should be notified immediately.

Study product usage errors are reportable irrespective of the presence of an associated AE, including:

- study product usage errors involving subject exposure to any of the study products;
- potential study product usage errors or uses outside of what is foreseen in the protocol that do or do not involve the participating subject.

Property of GSK Consumer Healthcare - Confidential

May not be used, divulged, published or otherwise disclosed without the consent of  
 GSKCH

CCI

Clinical Protocol Template v7.0

Page 40 of 100

If a study product usage error is accompanied by an AE, as determined by the investigator, the study product usage error and any associated adverse event(s) are to be captured in the eCRF AE form.

#### **6.2.2 Overdose**

Overdose is not likely to occur in this study. Limited quantities of the study products will be supplied and closely monitored by the site for each subject.

Overdose per se is not an AE. However, any clinical sequelae of an overdose should be reported as an AE (and serious adverse event (SAE), if appropriate). For reporting, follow the AE and SAE reporting instructions.

#### **6.3 Study Product Storage**

The investigator or designee must confirm appropriate temperature conditions have been maintained during transit for all study products received and any discrepancies are reported and resolved before use according to the supplied shipping documentation.

The investigator, or designee, will ensure that all study products are stored in a secured area with controlled access under required storage conditions and in accordance with applicable regulatory requirements, the product label and Clinical Study Supplies Checklist.

Site systems must be capable of measuring and documenting (for example, via a log), at a minimum, daily minimum and maximum temperatures for all site storage locations (as applicable, including frozen, refrigerated, and/or room-temperature products). This should be captured from the time of first product receipt throughout the study. Even for continuous monitoring systems, a log or site procedure that ensures active daily evaluation for excursions should be available. The operation of the temperature-monitoring device and storage unit (for example, refrigerator), as applicable, should be regularly inspected to ensure it is maintained in working order.

Any excursions from the product-label storage conditions should be reported to appropriate site staff upon discovery and communicated to sponsor as soon as possible. The site should actively pursue options for returning the product to the storage conditions as described in

Property of GSK Consumer Healthcare - Confidential

May not be used, divulged, published or otherwise disclosed without the consent of  
GSKCH

CCI

Clinical Protocol Template v7.0

Page 41 of 100

the labeling, as soon as possible. Excursions from the storage requirements, including any actions taken, must be documented as a protocol deviation and reported to the Sponsor.

Once an excursion is identified, the affected product (or products) must be quarantined and not used until the sponsor provides documentation of permission to use. Use of any of the affected product(s) prior to sponsor approval will be considered a protocol deviation.

Site staff will instruct subjects on the proper storage requirements for all take-home products.

#### **6.4 Study Product Accountability**

All products supplied are for use only in this clinical study and should not be used for any other purpose.

All study products must be received by a designated person at the study sites, handled and stored safely and properly, and kept in a secure location to which only permitted staff have access. Upon receipt, all study products should be stored according to the instructions specified on the product labels. Study products are to be dispensed only to subjects enrolled in the study in accordance with the protocol, by authorised site staff.

The investigative site must maintain adequate records documenting the receipt, use, loss, or other disposition of all the product supplies. All study products will be accounted for using the study product accountability form/record. The investigator is responsible for study product accountability, reconciliation, and record maintenance.

Subjects will return used and unused tubes of the acclimatisation toothpaste to the study site at their Baseline visit (Visit 2). Subjects will return used and unused tubes of their assigned study toothpaste to the study site at their last visit (for most subjects this will be Visit 6). Study product return will be documented using the study product accountability form/record.

The accountability records must be available for inspection by the study monitor during the study. Monitoring of product accountability will be performed by the monitor during site visits and at the completion of the study.

Property of GSK Consumer Healthcare - Confidential

May not be used, divulged, published or otherwise disclosed without the consent of  
GSKCH

CCI

Clinical Protocol Template v7.0

Page 42 of 100

#### **6.4.1 Destruction of Study Product Supplies**

At the conclusion of the study, the investigator or an appropriate designee, and a representative of GSK CH (study monitor) will inventory all used and unused study products and sundry items. The study product accountability record for returned study products will then be completed. All study product (used and unused) for this clinical study (including empty containers), will be returned for destruction to the GSK CH Clinical Supplies Department or designated vendor using the return instructions provided.

Return and destruction instructions for sundry items are provided in Table 6-2.

#### **6.5 Blinding and Allocation/Randomisation**

All subjects will be centrally randomised to one of the four study products using an Interactive Response Technology (IRT). Before the study is initiated, training, login information and directions for the IRT will be provided to the study site. Study products will be dispensed according to the instruction received through the IRT at the appropriate study visits.

Returned study products should not be re-dispensed to any subject. This study is described as examiner-blind (the subjects, investigator, clinical examiner and monitor will be blinded to product received). Site staff, the study statistician, data management staff, other employees of the Sponsor and vendors acting on behalf of the sponsor, who may influence study outcomes will also be blinded to the product allocation.

To ensure the clinical examiner remains blinded throughout the study:

- site staff involved in the dispensing of study product and the supervision of onsite product usage will work in a separate area;
- the examiner will not be permitted in any area where study product is stored, dispensed, or in use;
- study subjects will be instructed not to remove study product from the opaque bags it is provided in outside of the dispensing room, while at the study site;
- dispensing staff and on-site brushing supervisors will not be involved in any safety/product performance assessments during the study.

Property of GSK Consumer Healthcare - Confidential

May not be used, divulged, published or otherwise disclosed without the consent of  
GSKCH

CCI

Clinical Protocol Template v7.0

Page 43 of 100

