## 4 STUDY DESIGN

### 4.1 Overall Design

This will be a PoP, single centre, 8-week, randomised, controlled, examiner blind, parallel design, stratified (by maximum Baseline Schiff sensitivity score of the two selected test teeth) clinical study in healthy subjects with sensitive teeth.

To help minimise the potential impact of 'placebo'/'no treatment' effects, and to standardise oral hygiene practices, an acclimatisation period (2-4 weeks) will be included between the Screening and Baseline assessments. Subjects who meet all study criteria at both Screening and Baseline visits will be randomised to one of the 4 study products.

In line with widely recommended oral hygiene practice and typical consumer habit, study subjects will be requested to brush their teeth for one timed minute twice daily (morning

Property of GSK Consumer Healthcare - Confidential

May not be used, divulged, published or otherwise disclosed without the consent of  
 GSKCH

CCI

Clinical Protocol Template v7.0

Page 23 of 100

and evening) with their assigned study toothpaste, covering the toothbrush head with full ribbon of toothpaste (approximately 1.5 g) on each brushing occasion.

Two independent stimulus-based (tactile and evaporative) measures of tooth sensitivity will be employed.

- A tactile stimulus will be administered using a constant pressure probe (Yeaple Probe (Polson et al., 1980)). Subject response will determine the tactile threshold in grams (g).
- An evaporative (air) stimulus will be administered using a dental air syringe. Subject response will be evaluated using the Schiff sensitivity scale (Schiff et al., 1994).

Sensitivity to tactile and evaporative (air) stimuli will be assessed at Screening (Visit 1) and then at various time points across the 8-week usage period - Baseline (Day 0), Day 3 and Weeks 2, 4 and 8. A single clinical examiner will assess both measures for the duration of the study for all study subjects. On completion of the Baseline assessments, the clinical examiner will select two 'test teeth' from those that qualified at Screening and Baseline, for assessment of tactile and evaporative (air) sensitivity at all subsequent visits. In addition, the remaining 'eligible teeth' identified as sensitive to both tactile and evaporative (air) stimuli at Screening will be assessed for evaporative (air) sensitivity only at Day 3 and Weeks 2, 4 and 8.

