## 4.2 Scientific Rationale for Study Design

The study will investigate the ability of an experimental combination toothpaste containing 3% weight/weight (w/w) PVM/MA + 5% w/w KNO3 (Test Product), a 3% w/w PVM/MA only toothpaste (Comparator 1), a 5% w/w KNO3 only toothpaste (Comparator 2) and a regular fluoride toothpaste with no known anti-sensitivity properties (negative control) to protect sensitive teeth from DH. Trends in sensitivity measures over time (from Baseline to 8 weeks) will be investigated for each product group as the primary objective. Inter-product comparisons will be investigated as secondary objectives; comparisons between the Test and Comparator toothpastes will be of particular interest to explore if the combination toothpaste provides enhanced sensitivity protection.

The randomised, controlled, examiner-blind, parallel design selected for this study follows the recommended approach for investigating the performance of sensitivity products.

Use of two independent stimulus-based (tactile and evaporative (air)) measures of tooth sensitivity is in line with published recommendations for the design and conduct of sensitivity clinical studies. The selection of two 'test teeth' to evaluate changes in DH is also common practice in sensitivity studies (Schiff et al., 1994). Eligible subjects will be stratified after the Baseline assessments according to the maximum Schiff sensitivity score of their two selected 'test teeth' to ensure product groups are balanced for sensitivity severity.

Study subjects will be aged between 18 and 65 years; DH most frequently occurs between the ages of 20 and 40 years and is known to decrease with age above 40 years (Bartold, 2006, West et al., 2014, Dababneh et al., 1999).

According to ICH guidelines, for a study to be classed as truly double blind, not only does the examiner (and any appropriate member of staff who may be involved in the dispensing of products, analysis of data etc.) need to be blinded as to the product the subject receives, but the products under test must be identical in every way (colour, flavour, appearance, packaging). Given it is almost impossible to ensure identical appearance, taste and packaging for the toothpastes evaluated in oral care studies, the level of product blinding for this study is described as 'examiner blind'. Study toothpastes will be supplied in over-wrapped tubes. The blind will be maintained by staff involved in dispensing, brushing

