Property of GSK Consumer Healthcare - Confidential

May not be used, divulged, published or otherwise disclosed without the consent of  
 GSKCH

CCI

Clinical Protocol Template v7.0

Page 25 of 100

instruction and supervised brushings not being involved in the clinical examinations and study products being provided to subjects in blinded packs.

The DHEQ is a validated, condition-specific measure of the impacts of tooth sensitivity on everyday life; it has been shown to have good psychometric properties in both the general population and in a clinical sample of subjects with sensitive teeth (Boiko et al., 2010, Baker et al., 2014). A short form of the DHEQ (DHEQ-15) has also been developed and validated (Machuca et al., 2014) and will be included in this study to evaluate product performance in a clinically diagnosed DH population. In addition, an NRS will be used to monitor changes in the level of subject-perceived discomfort associated to tooth sensitivity at the same time points as the DHEQ.

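### The negative control is the run-in toothpaste, so only control subjects may notice no change; neither document addresses this, and subjects are not asked to keep quiet about their paste to the examiner

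*Protocol*

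**What the plan says.** **Products.** Protocol Table 6-1, the protocol synopsis and SAP Table 1-2 all name "Colgate Cavity Protection" for both the acclimatisation product and the negative control. The Test Product and Comparators 1 and 2 have no trade name.

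**Packs.** Under Protocol 6.1.1, Test and comparator pastes are "filled into plain white tubes by GSK CH with a study label affixed", whereas "the acclimatisation and control toothpastes will be supplied in their commercial packs". Every tube, run-in included, is then overwrapped in white vinyl to hide branding, and Section 4.2 speaks of "study products being provided to subjects in blinded packs".

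**Blinding.** Section 6.5 calls the study examiner-blind and explains that "the subjects, investigator, clinical examiner and monitor will be blinded to product received". Section 4.2 gives the reason for the label: "it is almost impossible to ensure identical appearance, taste and packaging for the toothpastes evaluated in oral care studies".

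**Protecting the examiner's blind.** Section 6.5 lists four steps: a separate area for dispensing and supervised brushing, no examiner access to product areas, opaque bags kept closed outside the dispensing room, and no assessment role for dispensing or brushing staff. Section 9 largely repeats them.

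**Run-in and examiner.** Section 4.1 justifies the 2-4 week acclimatisation period thus: "To help minimise the potential impact of 'placebo'/'no treatment' effects, and to standardise oral hygiene practices". It adds: "A single clinical examiner will assess both measures for the duration of the study for all study subjects".

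**The concern.** Three arms meet a new paste at Baseline and one does not. The overwrap hides the brand, but no passage says that the pastes match in taste, colour or texture, or that the tubes match in shape. A control subject is therefore placed differently from everyone else: nothing may seem to have changed.

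This could matter in two ways.

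- **Through the subject.** The endpoints depend on how subjects respond. Tactile threshold is a yes/no answer (Protocol 9.1.4). Schiff is graded from physical, behavioural and verbal reactions (9.1.5), and the number of sensitive teeth is counted from Schiff. DHEQ and NRS are self-reported. If recognition lowers or raises expectation in one arm only, Test versus negative control contains that effect together with any product effect.
- **Through the examiner.** One person scores everyone. A remark that the paste is the same as before could identify the control arm to an examiner who knows the protocol. No step in 6.5 guards against such a remark.

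The run-in does not settle this. It can reduce placebo and no-treatment effects before Baseline, but recognition that differs by arm arises only afterwards.

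**Working it through.** The point rests mainly on the text; the arithmetic gives its reach.

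**1. What the documents cover**

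| Question | Where looked | Found |
|---|---|---|
| Are run-in and control the same product? | Synopsis, Table 6-1, SAP Table 1-2 | Yes |
| Is imperfect masking of subjects acknowledged? | Protocol 4.2 | Yes, in general terms |
| Is the run-in/control identity discussed as a blinding issue? | Protocol 4.1, 4.2, 6.5; SAP | No |
| Are subjects asked not to mention their paste to the examiner? | Protocol 5.5, 6.5, 9 | No |
| Is recognition or a product guess recorded? | Diary (6.7), DHEQ (9.2.1), NRS (9.2.2), SAP Appendix 1 | No |

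**2. Exposure before randomisation.** Acclimatisation lasts 14 to 28 days with two brushings a day: 14 × 2 = 28 and 28 × 2 = 56. About 30 of 120 subjects then continue on that paste; 120 − 30 = 90 change.

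**3. Share of the planned tests.** SAP 4.4.2.1.2 and 4.4.2.2.2 each list three contrasts at four visits. With two endpoints (Schiff and tactile), 3 × 2 × 4 = 24 between-product tests. Test versus negative control is 1 × 2 × 4 = 8 of them.

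**4. The plan's precision figure.** Protocol 12.1 and SAP 1.4 give SD 0.7, n = 30 per group and ±0.261. Check: t(0.975, 29) × 0.7 / √30 = 2.045 × 0.1278 = 0.261. It reproduces. That is the precision of one group's mean. For a difference between two groups, SE = 0.7 × √(2/30) = 0.181 and the half-width is 1.981 × 0.181 = 0.358 (115 df: 120 subjects less four products and one covariate).

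**5. Illustration on an assumed bias.** The documents give no expectation effect, so the values of b below are assumptions, shown only for scale. Suppose there is no true difference and expectation favours Test by b Schiff units. The chance of a two-sided 5% result follows from the noncentral t distribution with 115 df and noncentrality b/0.181. SD 0.7 is used unreduced for covariate adjustment.

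| Assumed b | Noncentrality | Chance of p < 0.05 |
|---|---|---|
| 0 | 0 | 5.0% |
| 0.1 | 0.55 | 8.5% |
| 0.2 | 1.11 | 19.5% |
| 0.3 | 1.66 | 37.7% |

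**6. What a recognition question could show.** For a share estimated from 30 control subjects, the worst-case 95% half-width is 1.96 × √(0.25/30) = 0.179, about ±18 percentage points. For control (30) against the other arms (90), it is 1.96 × √(0.25/30 + 0.25/90) = 0.207, about ±21 points. These are sampling errors only. They do not cover errors of recall.

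**The case against.** The case against is substantial, and much of it stands.

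**Imperfect masking is already disclosed.** A reader might infer that 6.5, which lists subjects as blinded, contradicts 4.2, which says identical pastes are almost impossible. The documents do not support that. Section 6.1.2 has products dispensed to subjects in blinded fashion, and 6.5 goes on to speak of product allocation; the ordinary reading is that allocation is not disclosed. What is missing is a sentence on one specific cause, a difference that singles out one arm.

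**The diary is not a demonstrated leak.** A reader might infer that the examiner could learn the product from diary notes, since 8.3 lets the investigator or a designee review them. The text points the other way. Tube check and diary review form one step in 8.2.1 to 8.2.3, and 6.7 gives it to study staff. Subjects may not take product out of its bag outside the dispensing room, and the examiner is barred from product areas. A control subject with an unchanged paste also has no evident problem to write down. No claim is made about the diary.

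**Recognition is not expectation.** Noticing that the paste is unchanged matters only if the subject believes that paste to be inactive or the control. Section 8.1.1 provides an ingredient list at consent, but the consent pages are not available. An instruction about discussing the paste could also sit in subject-facing material not seen here. This stands, and it is why the effect is stated as possible. Section 6.5 is nonetheless where the protocol lists its safeguards for the examiner's blind.

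**The study is exploratory.** The primary analysis is descriptive (SAP 4.4.1.2), there is no formal success criterion (Protocol 3), and 4.2 singles out Test versus the comparators for interest. This also stands and limits the weight of the point. Even so, the control contrast is among the planned tests, the negative control is part of the informal expectation in Section 3, and Section 2.1 says the data will help design later studies.

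**Conclusion.** The point holds, with modest reach. The run-in and control pastes are the same, one arm alone may notice no change, neither document addresses this, and no listed safeguard covers what subjects say to the single examiner. The exposed contrast is Test versus negative control, 8 of 24 planned between-product tests. Test versus Comparator 1 and 2 is less exposed because all three of those pastes are new at Baseline.

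A reader might go further and infer that control subjects are unblinded or that the control contrast is biased. The documents do not support that: whether recognition occurs, whether it changes expectation, in which direction and by how much cannot be derived. The table of assumed biases shows scale, not a forecast.

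The conclusion assumes that the pastes can be told apart in use, which Section 4.2 makes plausible but does not establish for these products; that the examiner knows which paste is the control; and that no instruction outside the supplied text already covers remarks to the examiner. This is a cheap improvement to conduct and reporting. It is no ground for changing the products or the run-in.

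**What to change.** 1. **Protocol 6.5, list of steps.** Add that subjects are instructed at dispensing, and reminded before each examination, not to discuss their toothpaste with the examiner.
2. **Protocol 6.5, wording.** State that allocation is not disclosed to subjects, that the pastes are not identical, and that the control is the acclimatisation paste.
3. **SAP 4.4.2.** State that Test versus negative control may include an expectation effect of unknown size and direction, and that Test versus Comparator 1 and 2 is less exposed.
4. **Optional.** After the subject's last assessment at Visit 6, have dispensing staff ask whether the study paste was the same as the acclimatisation paste (same / different / unsure), and tabulate the answers by product. Asked then, the question cannot alter that subject's endpoints. Describe the table only as a rough indicator: subjects would be recalling a paste from about 8 weeks earlier, and someone who felt no benefit may answer 'same' for that reason. A reader should not infer that it makes the control contrast interpretable.

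**Cost.** One instruction and a few sentences; with the option, also one question, one eCRF field and one table. Products, arms, sample size, visits and planned tests stay as they are. The downside is a slightly less favourable description of the control contrast. Step 1 closes one route to the examiner. None of the steps removes an expectation effect within subjects.
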